An individual subject may not receive any therapeutic benefit from participating in an investigational study however, by contributing to medical research, others will be helped. All subjects participating in the study will receive physical examinations, various laboratory tests, ECGs and a systematic evaluation of their condition. Ecopipam may help improve symptoms for participants.

Protocol EBS-101-TD-301 Version 9.0, 05 March 2024

5.3.3. Methods to Minimize Risks

The following steps are incorporated in the protocol to minimize risks to subjects:

- Subjects will be screened by an Eligibility Review study team for determination of their appropriateness to participate.
- All subjects will be evaluated for safety at least every four weeks while receiving study medication.
- All assessment instruments will be administered by raters trained by the rater training group for the relevant scale/instrument. To the extent possible, the same caregiver(s) should complete the questionnaires and interviews from the same rater at each applicable visit.
- All subjects will be evaluated using the following scales to assess possible worsening of other psychiatric symptoms or other side effects:
 - Columbia Suicide Severity Rating Scale (C SSRS) for all subjects
 - Children's Depression Rating Scale (CDRS-R) for children and adolescents
 - Patient Health Questionnaire-9 (PHQ-9) for adults
 - Pediatric Anxiety Scale (PARS) for children and adolescents
 - Hamilton Rating Scale for Anxiety (HAM-A) for adults
 - Extrapyramidal Symptom Ra ing Scale (ESRS) for all subjects
 - Children's Yale-Brown Obsessive-Compulsive Scale-II (CY-BOCS-II) for children and adolescents
 - Yale-Brown Obsessive-Compulsive Scale-II (Y-BOCS-II) for adults
 - Swanson, Nolan and Pelham Questionnaire (SNAP-IV-26) for children and adolescents
 - Conners Adult ADHD Rating Scale Self Report, Short Version (CAARS-S:S) for adults

In summary, ecopipam is a new chemical entity with a novel mechanism of action that has clinical evidence that it may be of therapeutic benefit to subjects with TD. There is also evidence that it is likely to have lower side effect burden (for EPS- and other movement-related adverse events, adverse metabolic events and lack of weight gain) than the currently used D2-receptor antagonists. The protocol has processes to minimize potential risks from study medication that participants may be exposed to such that risks from the study balance the potential benefits.

Protocol EBS-101-TD-301 Version 9.0, 05 March 2024

6. STUDY OBJECTIVES AND PURPOSE

6.1. Primary Objective

The primary objective of this study is to evaluate the maintenance of efficacy of ecopipam tablets in children (≥ 6 and ≤ 12 years of age) and adolescents (≥ 12 and ≤ 18 years of age with TD.

6.2. Secondary Objectives

The secondary objectives of this study are to evaluate the safety and tolerance of ecopipam dosed at 1.8 mg/kg/day (2 mg/kg/day ecopipam HCl) in children (\geq 6 and < 12 years of age), adolescents (\geq 12 and < 18 years of age), and adults (\geq 18 years of age) with TD, to evaluate the maintenance of efficacy of ecopipam in adults (\geq 18 years of age), and to characterize the pharmacokinetics (PK) of ecopipam in all subjects.

6.3. Exploratory Objective

To evaluate the population PK/pharmacodynamic (PD) relationships with ecopipam during the open-label Stabilization period of the study and additional exploratory endpoints listed in Section 11.3.

Protocol EBS-101-TD-301 Version 9.0, 05 March 2024

7. INVESTIGATIONAL PLAN

7.1. Overall Study Design

This is a multicenter study which includes an open-label period followed by double-blind, placebo-controlled, randomized withdrawal period in children (≥ 6 and ≤ 12 years of age), adolescents (≥ 12 and ≤ 18 years of age), and adult subjects (≥ 18 years of age) with TD.

After providing informed consent (adult subjects or caregivers to children/adolescents) and assent (children/adolescents) and following an up to 28-day Screening period, and with agreement by Eligibility Review by the study team, subjects will proceed to the Baseline visit (Day 1).

Eligibility Review is an evaluation and quality oversight process of subject eligibility. Sites will complete an Eligibility Review packet at Screening which includes key medical information (e.g., laboratory results, ECG, medical history, physical examination, concomitant medications), scales data (e.g., subject questionnaire responses), and any other information necessary to establish subject eligibility per protocol. A decision to enroll a subject will be made by the investigator only after the Eligibility Review is concluded. The investigator remains responsible for ensuring that subjects are eligible for enrollment.

At the Baseline visit, eligible subjects will be entered into an open-label Stabilization period and start a 4-week Titration phase to achieve a target steady-state dose of 1.8 mg/kg/day ecopipam (2 mg/kg/day ecopipam HCl) followed by an 8 week open-label maintenance phase.

During the open-label Stabilization period, subjects will return to the clinic at Baseline (Day 1) and Weeks 4, 8 and 12. Subjects will have a telephone visit at Week 2 to assess adverse events (AEs) and other safety parameters. Efficacy assessments will be conducted at Weeks 4, 8 and 12. PK samples will be collected at Weeks 4 and 8. A PK assessment may be collected at Week 12 if the Week 8 PK assessment is missed. Safety assessments will be conducted at all visits.

Responders to ecopipam, defined a those with ≥ 25% improvement from Baseline (Day 1) on the YGTSS-TTS at both Weeks 8 & 12 during the open-label Stabilization period, will be randomized to ecopipam 1.8 mg/kg/day (ecopipam HCl 2 mg/kg/day) or placebo in a 1:1 fashion and enter a double-blind Randomized-Withdrawal (R/WD) period at Week 12. Subjects randomized to placebo will be tapered off ecopipam in a blinded fashion in decrements of 22.4 mg/day (25 mg/day ecopipam HCl).

During the R/WD period, subjects will return to the clinic every week for the first 4 weeks and every 2 weeks thereafter (Weeks 13, 14, 15, 16, 18, 20, 22 and 24) and efficacy and safety assessments will be conducted at each of these visits.

Any subject meeting Relapse criteria, defined as loss of $\geq 50\%$ of the improvement experienced on the YGTSS-TTS from Baseline (Day 1) to the last visit of the open-label Stabilization period (Week 12), or initiation of additional medications to treat symptoms of TD, or requirement of hospitalization for worsening symptoms of TD will be withdrawn from blinded study medication (ecopipam or placebo).

Non-responders to ecopipam during the open-label Stabilization period at either Week 8 or Week 12, or Responders randomized to ecopipam who complete the R/WD period, or who meet

Relapse criteria during the R/WD period, or who discontinue the study prematurely for any reason will be tapered off ecopipam in decrements of 22.4 mg/day (25 mg/day ecopipam HCl) and will complete the Week 24/Relapse/ET visit. Subjects assigned to placebo will receive placebo taper down medication to preserve the blind.

Follow Up visits will be conducted in the clinic 7 and 14 days after the last dose of study medication followed by a telephone call 30 days after the last dose of study medication to determine any adverse events, with the exception of subjects who roll into the open-label extension study EBS-101-TD-391within 30 days of their last study drug.

Subjects who experience Relapse may be treated for their TD with medications recommended by the PI or referred back to their primary physician for treatment after completing Day 7 and 14 follow-up visits.

[figure not shown]
Responders to ecopipam who complete the R/WD period and who complete the Week 24/Relapse/ET visit and the Day 7 and 14 follow-up visits are eligible to enter the long-term open-label study EBS-101-TD-391. Subjects who meet the criteria for Relapse and complete the Week 24/Relapse/ET visit and the Day 7 and 14 follow-up visits will have the opportunity to enter the long-term open-label study..

In anticipation of reaching the target number of Relapse events, randomization into the double-blind R/WD period may be closed, at which time subjects in the open-label Stabilization period may continue in the study until the Week 12 visit Upon completion of the Week 12 visit, subjects will have the opportunity to enter the long-term open-label study, EBS-101-TD-391.

The Sponsor may elect to re-open randomization as required.

Once the target number of Relapse events is met, all subjects may enter the long-term open-label study EBS-101-TD-391 once the Week 24/Relapse/ET visit and the Day 7 and 14 follow-up visits has been completed.

The study will be considered completed once all subjects have completed the 30-Day telephone Follow Up call or enters the open-label study EBS-101-TD-391.

Protocol EBS-101-TD-301 Version 9.0, 05 March 2024

7.2. Number of Subjects

The planned number of Relapse events for the double-blind R/WD period is 49 for children and adolescents (age ≥ 6 to < 18 years of age). This number of events will provide 85% power to detect a difference between treatment groups, assuming a hazard ratio of 0.4 for Relapse and statistical testing at alpha level 0.05 (2-sided). Assuming the proportion of subjects who Relapse in the double-blind R/WD period is 65% in the placebo group and 34% in the ecopipam group, approximately 98 children and adolescent subjects (49 subjects per group) will be required to achieve this number of events. Subject enrollment will stop around the time that 49 Relapse events for children and adolescents are expected to have occurred. The number of Relapses among adults will not determine study completion.

To randomize 98 children and adolescent subjects (≥6 to < 18 years of age), approximately 196 child and adolescent subjects will need to be enrolled assuming the Responder rate in the open-label Stabilization period is 50%.

Adult subjects with TD who meet all inclusion criteria and none of the exclusion criteria are eligible to enroll in the study. Since the symptoms of TD sh w improvement with age and a majority of adult patients exhibit minimal symptoms or are asymptomatic, it is anticipated that a minority of study participants will be adults. Hence it is anticipated that approximately 40 adults with TD will enter the open-label Stabilization period of this study.

7.3. Treatment Assignment

Responders to ecopipam in the open-label Stabilization period will be randomized 1:1 to either ecopipam or matching placebo for the R/WD period. Randomization assignment will be stratified by weight.

7.4. Dose Adjustment Criteria

Study drug is packaged for titration up t the target dose based on the subject's weight at Baseline according to the following weight bands to better achieve the targeted 1.8 mg/kg/day ecopipam (2 mg/kg/day ecopipam HCl) target dose: \geq 18 to \leq 23 kg, \geq 23 to \leq 34 kg, \geq 34 to \leq 44 kg, \geq 44 to \leq 68 kg, \geq 68 to \leq 83 kg, \geq 83 kg. Those who cannot tolerate the target dose will be withdrawn from study. Dose assignment (based on weight) will not change during the duration of the study even if subject's weight changes. Study drug is packaged for taper down in decrements of 25 mg/day until off study drug. See Section 10.5 for direction on administration of study drug.

7.5. Criteria for Subject Study Discontinuation

A subject may elect to discontinue from the study at any time for safety or personal reasons. All subjects who discontinue from the study should complete the early termination procedures.

Any subject with a new positive response on questions 4 and/or 5 of the Columbia Suicide Severity Rating Scale (C-SSRS) will be immediately discontinued and evaluated for risk.

Any subject with a CDRS-R or PHQ-9 assessment indicative of the onset of a new depressive episode at any visit can be discontinued from study participation at the discretion of the

Protocol EBS-101-TD-301 Version 9.0, 05 March 2024

Investigator. The Investigator will perform suicide risk assessment in subjects who respond positively to PHQ-9 question 9.

Subjects will be discontinued due to attempted suicide or suicidal behavior, oculogyric crisis, neuroleptic malignant syndrome, new onset seizures, serotonergic syndrome, or tardive dyskinesia. Subjects will also be discontinued if there are any adverse events that are Grade 4 (life-threatening consequences; urgent intervention indicated) in severity per CTCAE version 5.

Subjects who discontinue early from the study will be evaluated for one of these primary reasons: AE(s), lost to follow-up, subject choice, inadequate therapeutic effect, loss of efficacy, and administrative/other. In addition to the primary reason, the subject may have indicated one or more of these reasons as secondary reasons for discontinuation. Study disposition information will be collected on the CRF.

Subjects who discontinue treatment for any reason, other than an SAE (even if the SAE is not treatment related) or an AE (unless the AE can be determined to be unrelated to treatment), may be replaced only after consultation with Sponsor or its designee

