During the open-label Stabilization period, subjects will return to the clinic at Baseline (Day 1) and Weeks 4, 8 and 12 after Baseline. Subjects will have a telephone visit at Week 2 to assess adverse events (AEs) and other safety parameters. Efficacy assessments will be conducted at Weeks 4, 8 and 12. PK assessments will be conducted at Weeks 4 and 8. A PK assessment may be conducted at

Protocol EBS-101-TD-301 Version 9.0, 05 March 2024

Week 12 if the Week 8 PK assessment is missed. Safety assessments will be conducted at all visits including the telephone visit at Week 2.

Responders to ecopipam, defined as those with \geq 25% improvement from Baseline on the YGTSS-TTS (Yale Global Tic Severity Scale-; Total Tic Score) at both Weeks 8 & 12 during the open-label Stabilization period, will be randomized to ecopipam 1.8 mg/kg/day (2 mg/kg/day ecopipam HCl) or placebo in a 1:1 fashion and enter a double-blind Randomized-Withdrawal (R/WD) period at Week 12. Subjects randomized to placebo will be tapered off ecopipam in a blinded fashion in decrements of 22.4-mg/day (25-mg/day ecopipam HCl).

During the R/WD period, subjects will return to the clinic every week for the first 4 weeks and every 2 weeks thereafter (Weeks 13, 14, 15, 16, 18, 20, 22 and 24) and efficacy and safety assessments will be conducted at each of these visits. Any subject meeting Relapse criteria, defined as the loss of ≥50% of the improvement experienced on the YGTSS-TTS from Baseline (Day 1) to the last visit of the open-label Stabilization period (Week 12), or initiation of additional medications to treat symptoms of TD, or requirement of hospitalization for worsening symptoms of TD will be withdrawn from blinded study medication (ecopipam or placebo).

Non-responders to ecopipam during the open-label Stabilization p riod at either Week 8 or Week 12, Responders to ecopipam who complete the R/WD period, any subject who meets Relapse criteria during the R/WD period, and any subject who discontinues the study prematurely due to any reason will be tapered off ecopipam in decrements of 22.4-mg/day and will complete the Week 24/ Relapse/ET visit. Subjects assigned to placebo will receive placebo taper down medication to preserve the blind.

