- Those who weigh $>68 \le 83$ kg will receive 134.4 mg (150 mg ecopipam HCl) daily.
- Those who weigh >83 kg will receive 179.2 mg (200 mg ecopipam HCl) daily.

All doses will be administered once daily in the evening without regard to meals.

Non-responders to ecopipam during the open-label Stabilization period, subjects randomized to placebo during the R/WD period, responders to ecopipam who complete the R/WD period, any subject who meets Relapse criteria during the R/WD period, and any subject who discontinues the study prematurely due to any reason will be tapered off ecopipam in decrements of 22.4 mg/day (25 mg ecopipam HCl) until off drug; signs or symptoms of wi hdrawal, abuse and dependence will be monitored. Subjects assigned to placebo will receive placebo taper down medication to preserve the blind.

Duration of treatment:

Eligible subjects will receive open-label ecopipam tablets for up to 12 weeks. Subjects who qualify as Responders will be randomized at Week 12 to receive either ecopipam tablets or matching placebo for up to 12 weeks for a total of up to 24 weeks of treatment.

Reference therapy, dosage, and mode of administration:

Placebo-controlled, matching placebo tabl ts given by mouth (PO) in the evening.

Criteria for evaluation:

Efficacy:

Confidential

Primary Efficacy Endpoint:

• Time from Randomization (Week 12) to Relapse in subjects ≥ 6 and < 18 years for ecopipam compared to placebo during the double-blind, R/WD period.

Secondary Efficacy Endpoint:

• Time from Randomization (Week 12) to Relapse in all subjects irrespective of age for ecopipam compared to placebo during the double-blind R/WD period.

Exploratory Efficacy Endpoints:

- Time from Randomization (Week 12) to a worsening by at least one category of the CGI-TS-S in subjects ≥6 and < 18 years for ecopipam compared to placebo during the double-blind R/WD period. If there is a strong correlation of this endpoint with Relapse criteria based on the YGTSS-TTS, it may be considered as a secondary endpoint with agreement from Health Authorities.
- Time from Randomization (Week 12) to a worsening by at least one category of the CGI-TS-S in all subjects for ecopipam compared to placebo irrespective of age. If there is a strong correlation of this endpoint with Relapse criteria based on the YGTSS-TTS, it may be considered as a secondary endpoint with agreement from Health Authorities.

Protocol EBS-101-TD-301 Version 9.0, 05 March 2024

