10.5. Administration

During the 4-week titration phase of the open-label Stabilization period, the following ecopipam doses will be administered PO for each of the weight bands (see Table 5):

Table 5: Proposed Dosing Regimen

| Weight (kg) | Wee | ek 1 | Week 2 | | We | ek 3 | Week 4 | | |
|-------------|--------------------|---------------------------|--------------------|---------------------------|--------------------|---------------------------|--------------------|---------------------------|--|
| | ecopipam mg/day | ecopipam HCl mg/day | ecopipam mg/day | ecopipam HCl mg/day | ecopipam mg/day | ecopipam HCl mg/day | ecopipam mg/day | ecopipam HCl mg/day | |
| ≥18 - ≤23 | 11.2 | 12.5 | 22.4 | 25 | 33.6 | 37.5 | 33.6 | 37.5 | |
| >23 - ≤34 | 11.2 | 12.5 | 22.4 | 25 | 33.6 | 37.5 | 44.8 | 50 | |
| >34 - ≤44 | 11.2 | 12.5 | 22.4 | 25 | 44.8 | 50 | 67.2 | 75 | |
| >44 - ≤68 | 22.4 | 25 | 44.8 | 50 | 67.2 | 75 | 89.6 | 100 | |
| >68 - ≤83 | 22.4 | 25 | 44.8 | 50 | 89.6 | 100 | 134.41 | 150¹ | |
| >83 | 22.4 | 25 | 44.8 | 50 | 89.6 | 100 | 179.2 ² | 200^{2} | |

¹ 134.4 mg ecopipam dose (150 mg ecopipam HCl) given as two tablets containing 67.2 mg ecopipam (75 mg ecopipam HCl) each.

Subjects who do not tolerate the dose titration up to the full designated dose for their weight stratum will be discontinued from the study. These subjects will be tapered off their current dose of study drug according to their weight stratum.

During Weeks 4 to 12 of the open-label maintenance phase and for Responders in this period who are randomized to ecopipam for the 12-week R/WD period, the following ecopipam HCl doses will be administered f r each of he weight bands:

- Those who weigh $\ge 18 \le 23$ kg will receive 33.6 mg (37.5 mg ecopipam HCl) daily.
- Those who weigh >23 <34 will receive 44.8 mg (50 mg ecopipam HCl) daily.
- Those who weigh >34 \(\le 44 \) will receive 67.2 mg (75 mg ecopipam HCl) daily.
- Those who weigh >44 ≤68 kg will receive 89.6 mg (100 mg ecopipam HCl) daily.
- Those who weigh >68 \le 83 kg will receive 134.4 mg (150 mg ecopipam HCl) daily.
- Those who weigh >83 kg will receive 179.2 mg (200 mg ecopipam HCl) daily.

All doses will be administered PO once daily in the evening without regard to food. Subjects who have changes in weight during the study will not have their doses adjusted for the duration of the study.

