Responders who are randomized to placebo for the 12-week R/WD period will taper off ecopipam in decrements by 22.4 mg/day (25 mg/day ecopipam HCl) until off study drug. For the remainder of the R/WD period, these patients will receive matching placebo tablets.

Any subject randomized to placebo who meets Relapse criteria during the R/WD period, or who discontinues the study prematurely due to any reason, will receive a taper kit of matching

² 179.2 mg ecopipam dose (200 mg ecopipam HCl) given as two tablets containing 89.6 mg ecopipam (100 mg ecopipam HCl) each.

| Emalex Biosciences, | Inc. |
|---------------------|------|
| Ecopipam | |

Protocol EBS-101-TD-301 Version 9.0, 05 March 2024

placebo with the same number of tablets as subjects in the same weight band receiving blinded ecopipam to preserve the blind. All subjects will be monitored for signs or symptoms of withdrawal, abuse and dependence.

Non-responders to ecopipam during the Stabilization period, or Responders randomized to ecopipam who complete the R/WD period, or who meets Relapse criteria during the R/WD period, or who discontinues the study prematurely due to any reason will be tapered off ecopipam in decrements of 22.4 mg/day (25 mg/day ecopipam HCl) until off drug. All subjects will be monitored for signs or symptoms of withdrawal, abuse and dependence.

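### The end-of-treatment taper is not reconciled with the safety withdrawals in Protocol 7.5 and 8.3, and SAP Section 12 has no off-drug class for adverse events

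*Protocol*

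**What the plan says.** **Withdrawal.** Protocol 7.5 states: "Subjects will be discontinued due to attempted suicide or suicidal behavior, oculogyric crisis, neuroleptic malignant syndrome, new onset seizures". The sentence goes on to serotonergic syndrome and tardive dyskinesia, and the next adds any Grade 4 adverse event. Only new positive answers to C-SSRS items 4 or 5 carry a word on timing: such a subject "will be immediately discontinued and evaluated for risk". Section 8.3 repeats the list and, in the same paragraph, allows the investigator or the subject to halt study treatment on safety or personal grounds.

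**Dosing afterwards.** Section 10.5 covers non-responders, ecopipam-arm completers and subjects who relapse, "or who discontinues the study prematurely due to any reason will be tapered off ecopipam in decrements of 22.4 mg/day". The synopsis says the same twice (for example "any subject who discontinues the study prematurely due to any reason will be tapered off ecopipam in decrements of 22.4 mg/day"), as do 7.1 and SAP 4.1 and 4.5. For those who cannot tolerate titration, 10.5 says: "These subjects will be tapered off their current dose of study drug according to their weight stratum". A placebo-arm subject who relapses "or who discontinues the study prematurely due to any reason, will receive a taper kit of matching" placebo tablets.

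**Adverse-event timing.** SAP 8.2 defines four periods, with taper-down (TDAE) and off study drug (ODAE) as separate classes. SAP Section 12 defines timing-specific events again, with five milestones. The last is Down-titration, which begins after Week 24 or at early termination and has no stated end. AE table 15 in SAP 12.1 repeats those five. AE table 9 covers the safety follow-up by time, using windows counted from first dose that stop at Day 184.

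**The concern.** Section 7.5 decides who leaves the study, and 10.5 decides what they swallow next. Read together, a subject on ecopipam withdrawn for neuroleptic malignant syndrome or a first seizure goes by default onto a descending course of the same drug. The documents treat several of these events as plausibly drug-related. SAP 16.5 lists seizures, neuroleptic malignant syndrome, oculogyric crisis, tardive dyskinesia and suicidality among potential dopamine-antagonist effects. A history of seizures (other than febrile seizures more than two years before Screening) or of neuroleptic malignant syndrome bars entry (exclusion criteria 15 and 16). What is at stake is the safety of a small number of mostly pediatric subjects.

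The SAP matter is about reporting. Subjects are monitored for withdrawal signs, and 16.5 names tardive dyskinesia associated with withdrawal, so whether a late event arose during the taper or after the last dose is a question the tables should answer. Table 15 as defined cannot.

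**Working it through.** **1. Is there an exception to the taper?** The taper sentences in the synopsis, 7.1, 10.5, SAP 4.1 and SAP 4.5 contain none. SAP 4.6 defers to the protocol. Section 7.5 names adverse events among the reasons for discontinuing, and 10.5 tapers even subjects who cannot tolerate titration, so a discontinuation for an adverse event is within the rule. The only relief is the 8.3 permission, which is optional and does not mention the taper.

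**2. How much further ecopipam?** Inputs: maintenance doses and the 22.4 mg decrement from 10.5. Assumption: the first taper dose is already one decrement lower. Remaining levels are d − 22.4, d − 44.8, and so on while above zero. Because step length is not stated, the total is shown for one-day and seven-day steps.

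| Weight band (kg) | Maintenance (mg/day) | Levels left | Number | Total, 1-day steps (mg) | Total, 7-day steps (mg) |
|---|---|---|---|---|---|
| 18 to 23 | 33.6 | 11.2 | 1 | 11.2 | 78.4 |
| >23 to 34 | 44.8 | 22.4 | 1 | 22.4 | 156.8 |
| >34 to 44 | 67.2 | 44.8, 22.4 | 2 | 67.2 | 470.4 |
| >44 to 68 | 89.6 | 67.2, 44.8, 22.4 | 3 | 134.4 | 940.8 |
| >68 to 83 | 134.4 | 112.0, 89.6, 67.2, 44.8, 22.4 | 5 | 336.0 | 2352.0 |
| >83 | 179.2 | 156.8, 134.4, 112.0, 89.6, 67.2, 44.8, 22.4 | 7 | 627.2 | 4390.4 |

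With one-day steps, the total divided by the maintenance dose is 0.33, 0.5, 1.0, 1.5, 2.5 and 3.5 maintenance days.

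In titration, tapering from the current dose: Week 1 (11.2 or 22.4 mg) leaves 0 levels; Week 2 (22.4 or 44.8 mg) leaves 0 or 1; Week 3 (33.6, 44.8, 67.2 or 89.6 mg) leaves 1, 1, 2 or 3, at most 67.2 + 44.8 + 22.4 = 134.4 mg with one-day steps. A discontinuing placebo-arm subject given the matching-placebo kit gets 0 mg.

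**3. The two sets of adverse-event periods.**

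| SAP 8.2 | SAP Section 12 and table 15 |
|---|---|
| Open-label stabilization | Up-titration; open-label maintenance |
| Double-blind R/WD | R/WD Weeks 13-16; R/WD Weeks 17-24 |
| Taper down (TDAE) | Down-titration, no stated end |
| Off study drug (ODAE) | no counterpart |

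Events are collected for 30 days after treatment stops (Protocol 12.2.1.1). If Down-titration takes everything to the end of that period, its off-drug share for a subject with n taper levels of L days each is 30/(30 + nL):
- L = 1: 30/37 = 81% (n = 7) to 30/31 = 97% (n = 1).
- L = 7: 30/79 = 38% (n = 7) to 30/37 = 81% (n = 1).

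If Down-titration instead ends with the last taper dose, off-drug events have no row in table 15.

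**4. Does AE table 9 fill the gap?** Only in part. Table 3 puts follow-up at Days 170 to 199. The last listed window ends at Day 184, so for a completer on those nominal days 199 − 184 = 15 days fall in no window. Follow-up counted from Day 170 also takes in any taper days after Week 24.

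**The case against.** The strongest reply is that 8.3 already deals with this. It names the same events, lets the investigator stop treatment for safety in the same paragraph, and any competent physician would do so after neuroleptic malignant syndrome. That stands as far as it goes. A reader might infer that the protocol compels further ecopipam after these events; it does not, and the claim here is only about the written default. But the permission is optional and not linked to the taper, so a site must resolve the conflict itself during an emergency.

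A compulsory abrupt stop could also be questioned. The Phase 2b study reported no withdrawal signs but used down-titration, so an untapered stop is unmeasured, and SAP 16.5 lists a withdrawal-related dyskinesia. This stands, and is why the wording below keeps medical discretion. Nor does the 16.5 list match the events proposed for immediate stopping: serotonergic syndrome is absent from it, while tardive dyskinesia and suicidality are present. The choice of events is therefore a clinical judgement for the sponsor to confirm.

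On the SAP, a reader might infer that off-drug events are definitely counted as taper events. The SAP nowhere says so; they may instead be left out of table 15. Either way the two definitions conflict. Onset and last-dose dates are collected, so the information is not lost. Likewise, the 15 uncovered days apply only to a completer on Table 3's nominal days. Week 12 non-responders and early relapsers can fall wholly within the windows, while a taper after Week 24 pushes follow-up past Day 199.

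Finally, the contents list names an emergency-procedures page that was not in the text I read, so the absence of an exception is established only for the remaining sections.

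**Conclusion.** Both parts hold as matters of wording that should be corrected.

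1. The taper and the safety withdrawals are not reconciled. At maintenance dose the written default is 1 to 7 further levels of ecopipam: 11.2 to 627.2 mg if each lasts one day, 78.4 to 4390.4 mg if seven. These totals rest on an assumed step length and on the first decrement applying at once. The default is overridden if the investigator uses 8.3.
2. SAP 8.2 and Section 12 define timing-specific events differently, and table 15 has no off-drug class, so it cannot separate events on taper from events after the last dose.

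The first part should concern few subjects, although the documents give no expected rate for the listed events. The second touches every subject who ends treatment. Nothing here affects the primary efficacy analysis.

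**What to change.** **Protocol.** Add to 10.5, with a cross-reference in the synopsis, 7.1, 7.5, 8.3 and SAP 4.1 and 4.5 (SAP 4.6 needs no edit):

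> The taper does not apply when study drug is stopped for safety. After neuroleptic malignant syndrome, oculogyric crisis, new-onset seizure, serotonergic syndrome, or a Grade 4 AE judged possibly or probably related, study drug (ecopipam or placebo) is stopped at once unless the investigator documents a medical reason to taper. After the other 7.5 events, including C-SSRS items 4/5 and tardive dyskinesia, the investigator decides whether to taper.

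**SAP.** In Section 12 and table 15, replace Down-titration with the 8.2 classes:
- TDAE: from the first dose of the end-of-treatment taper kit to the last dose. If the first kit dose is not recorded, start at the Week 24/Relapse/ET visit date, when Table 3 dispenses drug. The blinded taper that starts at randomization in the placebo arm does not count.
- ODAE: after the last dose.

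Make the last by-time AE window open-ended instead of closing it at Day 184.

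**Cost.** Short text edits in several sections and one extra table column. Last-dose date is already needed for exposure in SAP 8.2, and applying the stop to both arms keeps the blind. The downside is that a few subjects stop without a taper, and the documents do not measure that risk.
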